12.1.7. Additional Investigator Responsibilities for SAEs

The safety data recorded in the CRF represent the official record of all AEs and SAEs reported in the study. The Investigator should comply with requests by the Medical Monitor or other Sponsor personnel to record the SAE on the subject’s AE CRF. Other supporting documents such as radiology reports, hospital discharge summaries, and autopsy reports should also be provided, when appropriate. Additionally, upon request by the Medical Monitor, the Investigator should provide input into the SAE narrative and provide timely information to ensure prompt follow up and closure of the SAE report.

The Investigator and supporting personnel responsible for subject care should discuss with the Medical Monitor any need for supplemental investigations of SAEs. The results of these additional assessments must be reported to the Medical Monitor.

12.1.8. Notification of Post-Treatment SAEs for Subjects Who Continue in the Study

Post-treatment SAEs that occur in subjects who remain in the study after investigational product has been discontinued must be reported to the Sponsor within 24 hours by following the instructions provided in [Section 12.1.5.2](#).

SAEs that occur in subjects who discontinue investigational product, initiate treatment with commercially available OCALIVA, and remain in the study must be reported to the Sponsor within 24 hours by following the instructions provided in [Section 12.1.5.2](#).

12.1.9. Notification of Poststudy SAEs

All SAEs that occur within 30 days following discontinuation from the study, whether or not they are related to the investigational product, must be reported to the Sponsor within 24 hours by following the instructions provided in [Section 12.1.5.2](#).

If an Investigator becomes aware of an SAE that may be attributable to the investigational product at any time after the end of the study, the Sponsor should be notified immediately (ie, within 24 hours) by following the instructions provided in [Section 12.1.5.2](#).

12.1.10. Follow-Up of AEs and SAEs

All AEs must be followed during the course of the study until the AE resolves, is no longer of clinical concern, has stabilized or is otherwise explained, or the subject is lost to follow-up.

AEs ongoing at the final visit that are deemed to be “possibly, probably, or definitely” related or of other clinical significance must be followed for as long as necessary to adequately evaluate the safety of the subject or until the event stabilizes, resolves, or is no longer of clinical concern. If resolved, a resolution date for the AE should be documented on the eCRF. The Investigator must ensure that follow-up includes any supplemental investigations indicated to elucidate the nature and/or causality of the AE. This may include additional laboratory tests or investigations, or consultation with other healthcare professionals, as considered clinically appropriate by the Investigator.

Drug-Induced Liver Injury or Disease Progression

All subjects showing possible drug-induced liver injury should be followed until all abnormalities return to normal or to the baseline state. Drug-induced liver injury may develop or progress even after the causative drug has been stopped. Results from drug-induced liver injury follow-up should be recorded in the eCRF. Note that longer follow-up can sometimes reveal an off-drug repetition of what had appeared to be drug-induced liver injury, indicating that liver injury was related to underlying liver disease.

Cholecystitis or Pancreatitis

At the time of consent for new subjects (or re-consent to the protocol amendments for ongoing subjects), subjects will be instructed to contact the investigational site if they experience any of the following signs and symptoms: nausea, vomiting, abdominal pain, diarrhea, weight loss, fever and chills, worsening or new fatigue, or weakness. Subjects will also be counseled to seek immediate medical assistance if they experience persistent severe abdominal pain.

In the event that cholecystitis and/or pancreatitis is suspected, Investigators will be instructed to promptly bring subjects into the clinic to undergo a complete evaluation, including a physical examination, and laboratory assessments [ie, amylase and lipase]). Investigators should refer to standard of care guidelines on suspected pancreatitis ([Banks 2012](#), [Greenburg 2015](#)). Diagnosis of acute pancreatitis includes 2 of the following:

- Abdominal pain (acute onset of a persistent, severe, epigastric pain often radiating to the back)
- Serum lipase activity (or amylase) at least 3 times greater than the upper limit of normal
- Characteristic findings of acute pancreatitis on computed tomography or magnetic resonance imaging

To ensure appropriate vigilance, amylase and lipase levels will be monitored monthly for 3 months after onset of symptoms, irrespective of whether a diagnosis of cholecystitis and or

pancreatitis is confirmed. The Investigator should contact the Medical Monitor upon awareness of the above (ie suspected or confirmed diagnosis). Results should be recorded promptly in the eCRF.

12.1.11. Pregnancy and Follow-Up

Pregnancies are not considered AEs in and of themselves; however, if a female study participant becomes pregnant while she is enrolled in the clinical study, she must interrupt treatment with investigational product immediately (see [Section 7.6](#) and the Sponsor must be notified within 24 hours of the Investigator's awareness of the pregnancy by completing the Pregnancy CRF in the EDC system and downloading and completing the Pregnancy Report Form. The Pregnancy Report Form must be emailed to [contact] or faxed to [contact]. The subject and neonate must be followed for outcome information and/or as considered appropriate by the Investigator and Sponsor.

The subject may restart investigational product when she is no longer pregnant or breastfeeding (if applicable) at the discretion of the Investigator and after discussion with the Medical Monitor. The subject must have a negative pregnancy test before restarting investigational product. If a subject's pregnancy is terminated early (planned or unplanned), she must have termination of the pregnancy confirmed by a serum β -hCG test before restarting investigational product.

Completing the Pregnancy Report Form is not a substitute for reporting an AE/SAE when and AE/SAE has occurred. In the situation when an AE/SAE has occurred, the AE/SAE reporting procedures described in [Section 12.1.5](#) must also be followed.

12.2. Other Safety Parameters

12.2.1. Medical History/Demographics

A complete medical history and PBC disease-specific history will be obtained from the subject at Screening. Smoking and alcohol consumption history and current habits will be recorded. Demographic characteristics (age, gender, race, and ethnicity) will be recorded.

12.2.2. Physical Examination

To assess for clinical findings, the Investigator or designee will perform a physical examination at the timepoints specified in the Schedule of Study Procedures ([Section 7.1.1](#)). A basic physical examination should be performed, including all body systems pertinent to the subject. Any clinically significant abnormality should be reported on the AE CRF page for findings that appear after consent, and on the medical history CRF for any finding present prior to consent. Information about smoking and alcohol consumption habits will be collected at the same (follow-up) timepoints as the physical exam.

12.2.3. Vital Signs

Vital signs will be assessed at indicated visits: height, weight, temperature, sitting heart rate, respiratory rate, and sitting blood pressure. When taking heart rate, respiratory rate, and blood pressure readings, subjects should be seated quietly for a minimum of 3 minutes before the readings are taken.

12.2.4. Electrocardiogram

Standard 12-lead ECGs will be collected at the Screening Visit 1, Month 12, and at EOT/EOS. The Investigator or designee will review the 12-lead ECG and findings will be recorded in the CRF as normal, abnormal but not clinically significant, or abnormal and clinically significant. Any clinically significant abnormality on ECGs should be reported on the AE CRF page.

Investigative sites must retain a copy of all 12-lead ECGs evaluated by the Investigator or designee. These ECGs must be clearly labeled with the subject's initials, Subject ID number, date, and time.

12.2.5. Subject Questionnaires

Information about the subject's PBC disease history (ie, date of diagnosis, treatment history, pruritus history, signs and symptoms, and including smoking history) will be collected during Screening. At subsequent study visits (see [Section 7.1.1](#)), subjects will be asked to complete the following questionnaires; they may be asked to initial and date to document confirmation of their responses, and the questionnaires should be filed in the subject's study records. These may require transcription to the CRF by study site staff.

- 5-D Pruritus Questionnaire: This is a questionnaire that has been validated in several different diseases. It assesses symptoms in terms of 5 domains: degree, duration, direction, disability and distribution ([Elman 2010](#)).
- Pruritus VAS: A Visual Analogue Scale (VAS) will also be used to assess pruritus in individual subjects.

12.2.6. Laboratory Assessments

Subjects will be instructed to attend any study or unscheduled laboratory visits (except Screening) in a fasted state, and subjects should remain fasted until their blood samples have been collected. At each visit, the Investigator or designee will verify that the subject has fasted for at least 8 hours and record fasting status in the source and CRF. If the subject reports having eaten (water is permitted) within 8 hours, the Investigator or designee will document accordingly in the source and CRF and remind the subject that fasting is required prior to all study visits.

Blood samples for serum chemistry and hematology will be collected at every visit as detailed in the Schedule of Study Procedures ([Section 7.1.1](#)). The number and volume of samples to be collected at each visit will be detailed in the laboratory manual.

Full instructions concerning the number and type of samples to be collected at each visit, the required sample volumes, sample collection methods, sample processing, labeling, and shipping will be provided by the central clinical laboratory in a study specific laboratory manual. All necessary collection supplies will be provided by the central laboratory and will be appropriately assembled for the specific evaluations required at each visit.

All subjects with laboratory tests containing clinically significant abnormal values are to be followed regularly until the values return to normal ranges; until a valid reason, other than investigational product-related AE, is identified; or until further follow up is deemed medically unnecessary.

Laboratory samples will be stored for a maximum of up to 1 year after the end of the study (depending on stability) in the event that retesting is required, and destroyed after 1 year if not analyzed.

The list of laboratory analytes to be tested is shown in Table 12, and the normal reference ranges for liver biochemistries are shown in [Appendix C](#).

Table 12: List of Laboratory Analytes to be Tested

Laboratory Assessment	Analyte
Serum Chemistry	Albumin, blood urea nitrogen (BUN), creatinine, direct bilirubin, total bilirubin, aspartate aminotransferase [AST, SGOT], alanine aminotransferase [ALT, SGPT], ALP, GGT, electrolytes [calcium, chloride, potassium, sodium], glucose, total protein, and blood lipids (total cholesterol, LDL, HDL and very low-density lipoprotein [VLDL] fractions and triglycerides [TG]), magnesium, phosphorus, bicarbonate, unconjugated (indirect) bilirubin, conjugated (direct) bilirubin, free fatty acids
Hematology	Hemoglobin, hematocrit, white blood count with differential, neutrophils, lymphocytes, monocytes, eosinophils, basophils, platelets, red blood cell count (including MCV, MCH, MCHC)
Coagulation	Prothrombin time (PT), partial thromboplastin time (PTT), international normalized ratio (INR)
Urinalysis	pH, specific gravity, total protein, glucose, ketones, bilirubin, blood, microscopic exam, urobilinogen, albumin, creatine, leucocytes, nitrates, albumin/creatinine ratio (if positive)
Markers of Cholecystitis and Pancreatitis	amylase and lipase
Biomarkers of Hepatic Fibrosis and/or Inflammation	IgM, C-reactive protein (CRP), TNF- α , FGF-19, CK-18, ELF, and others as determined during course of study
Genetics	DNA including single-nucleotide polymorphisms (SNPs) that may be involved in PBC; RNA
Other	OCA (parent and conjugates [glyco and tauro], OCA-glucuronide) and C4

The Investigator should manage subjects with clinically significant lipoprotein abnormalities using local standard of care procedures as appropriate after assessing the individual subject's total cardiovascular risk profile.

Urine-based β -hCG pregnancy tests will be performed in female subjects of childbearing potential per protocol specified visits. If a urine pregnancy test is positive, a serum pregnancy test must be performed to confirm the result. If positive, the Sponsor must be notified and the subject will be followed, as outlined in [Section 12.1.11](#) through pregnancy outcome.

MELD scores and Child-Pugh score will be calculated at screening, and at all visits based on serum chemistry and coagulation.

13. STATISTICAL METHODS

A statistical analysis plan (SAP), providing details about the specific planned analyses and hypothesis tests, will be prepared and approved by the Sponsor and its designees prior to the first interim analysis, propensity score determination, and unblinding of the double-blind subject treatment assignments.

13.1. Efficacy Analysis

13.1.1. Analysis Populations

The following subject populations will be evaluated and used for presentation and analysis of the data:

- The Intent-to-Treat (ITT) Population will include all randomized subjects who receive any amount of investigational product (OCA or placebo). The ITT Population will be the primary population used for efficacy analyses. Treatment assignment will be based on the randomized treatment.
- The Per Protocol (PP) Population will include all ITT subjects who do not have any major protocol violations that potentially affect the efficacy conclusion. Treatment assignment will be based on the randomized treatment.
- The Safety Population will include all subjects who received any amount of investigational product (placebo or OCA). The Safety Population will be the primary population used for safety analyses. Treatment assignment will be based on the treatment actually received.
- The PK Population will include all OCA subjects who have at least one confirmed fasted analyzable sample. Subjects must have been fasting for approximately 8 hours prior to the visit and must not have any major protocol deviations that potentially affect exposure levels. The PK population will be used for OCA PK analyses.
- The Overall Historical Control Population will include subjects from the United Kingdom (UK) -PBC Group and Global PBC Study Group databases with demonstrated comparability to randomized subjects in this clinical study (747-302) with respect to both subject characteristics and disease progression.
- The UK-PBC Historical Control Population will include subjects from the UK-PBC Group databases with demonstrated comparability to randomized subjects in this clinical study (747-302) with respect to both subject characteristics and disease progression.

- The Global PBC Historical Control Population will include subjects from the Global PBC Study Group database with demonstrated comparability to randomized subjects in this clinical study (747-302) with respect to both subject characteristics and disease progression.

13.1.1.1. Comparability of Historical Controls

Utilization of both historical control/observational databases (UK-PBC and Global PBC Study Group), with more than 6000 subjects each, allow for a rigorous subject level meta-analysis. The historical databases include long-term follow up, detailed subject-level information such as baseline clinical characteristics, longitudinal liver biochemistry, and long-term outcomes, and span a broad range of subject characteristics that may influence disease (disease state, age, gender, and regional differences in standard of care). Historical controls from both databases will be chosen based on the same study inclusion/exclusion criteria. Propensity score matching method will be utilized to select historical controls that match the treated subjects using available covariates. The adequacy of matching will be assessed by statistical methods described under [Section 13.1.8](#).

13.1.2. Determination of Sample Size

The target population is subjects who are at higher risk of liver-related clinical complications. Eligible subjects will have a diagnosis of PBC with bilirubin levels $>ULN$ and $\leq 5x ULN$ and/or $ALP > 3 \times ULN$. The following assumptions were used in sample size calculations:

- Exponential survival curves, placebo survival estimate of 0.6 at 8 years with a hazard ratio of 0.60, and total study duration of 10 years (from first subject enrolled), allowing for 4 years of subject accrual and 6 years of follow up.
- Subjects will be randomized in a 1:1 ratio to placebo or OCA.
- The 2 groups will be compared using a 2-sided log rank test at the 5% level of significance.
- Two interim analyses and one final analysis are planned. The first interim analysis will be performed when 50% of the target events are accrued and the second interim will be performed when 75% of the target events are accrued.
- A dropout rate of 10% is assumed

Based on the randomization ratio, significance level, and assumed hazard ratio, a total of 127 events (both groups combined) will provide 80% power to demonstrate a statistically significant difference between OCA and placebo on time to liver-related outcomes, including all-cause mortality.

In addition, based on the remaining assumptions stated above, it is estimated that approximately 428 subjects will be enrolled to attain 127 events.

13.1.2.1. Sample Size Monitoring

Conducting a long-term outcomes study given the low disease prevalence, relatively slow disease progression, and ethical considerations, which in combination will impact recruitment

and event rates, is inherently difficult. As stated in ICH E9, in long-term trials there is an opportunity to check the assumptions that underlay the original design and sample size calculations. The power stated above depends on the total number of events. Thus, the overall survival function can be estimated without unblinding.

Therefore, the aggregate event rate and sample size based on recruitment and retention will be evaluated quarterly in a blinded manner. This evaluation will determine if any increases in number of subjects are required in order to obtain a total of 127 adjudicated events for the final analysis in the combined groups. Specifically, the pooled number of events will be available during the study in a blinded manner, without any knowledge of the comparative efficacy in the treatment groups. This method for evaluating the sample size does not inflate the type I error rate. Additional subjects may be enrolled as appropriate.

13.1.3. Primary Efficacy Analysis

The primary efficacy endpoint will be the time to first occurrence of one of the following post-randomization:

- Death (all-cause)
- Liver transplant
- MELD score ≥ 15
- Hospitalization (as defined by a stay of 24 hours or greater) for new onset or recurrence of:
 - Variceal bleed
 - Hepatic encephalopathy (as defined by a West Haven score of ≥ 2)
 - Spontaneous bacterial peritonitis (confirmed by diagnostic paracentesis)
- Uncontrolled ascites (diuretic resistant ascites requiring therapeutic paracentesis at a frequency of at least twice in a month).

The primary efficacy analysis will compare OCA to placebo with respect to the primary efficacy endpoint using the ITT population. Only adjudicated events will be included in analyses. The 2 treatment groups will be compared using the log rank test stratified by the randomization stratification factor. Kaplan-Meier (KM) estimates of the distribution of the time-to-event will be tabulated and graphed by treatment group. The tabulation will include the KM estimate of the medians and corresponding 95% confidence intervals (CIs), if the medians can be estimated. The number and percent of subjects censored and with events will be presented. The hazard ratio and 95% CI will be determined based on a Cox regression model stratified by randomization strata to estimate the magnitude of the effect. The same analyses for primary efficacy endpoints will be performed for PP population as a sensitivity analysis.

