8.3. Subject Exclusion Criteria

1. History or presence of other concomitant liver diseases including:
 - Hepatitis C virus infection
 - Active hepatitis B infection; however, subjects who have seroconverted (hepatitis B surface antigen and hepatitis B e-antigen negative) may be included in this study after consultation with the Medical Monitor.
 - Primary sclerosing cholangitis
 - Alcoholic liver disease
 - Definite autoimmune liver disease or overlap hepatitis
 - Nonalcoholic steatohepatitis
 - Gilbert's Syndrome
2. Presence of clinical complications of PBC or clinically significant hepatic decompensation, including:

- History of liver transplant, current placement on a liver transplant list, or current MELD score >12. Subjects who are placed on a transplant list despite a relatively early disease stage (for example per regional guidelines) may be eligible as long as they do not meet any of the other exclusion criteria.
 - Cirrhosis with complications, including history (within the past 12 months) or presence of:
 - Variceal bleed
 - Uncontrolled ascites
 - Encephalopathy
 - Spontaneous bacterial peritonitis
 - Known or suspected hepatocellular carcinoma
 - Prior transjugular intrahepatic portosystemic shunt procedure
 - Hepatorenal syndrome (type I or II) or Screening (visit 1 or 2) serum creatinine >2 mg/dL (178 µmol/L)
3. Mean total bilirubin >5x ULN
 4. Subjects who have undergone gastric bypass procedures (gastric lap band is acceptable) or ileal resection or plan to undergo either of these procedures.
 5. Other medical conditions that may diminish life expectancy, including known cancers (except carcinomas *in situ* or other stable, relatively benign conditions).
 6. If female: plans to become pregnant, known pregnancy or a positive urine pregnancy test (confirmed by a positive serum pregnancy test by the central laboratory), or lactating.
 7. Known history of human immunodeficiency virus infection.
 8. Medical conditions that may cause non-hepatic increases in ALP (eg, Paget's disease or fractures within 3 months).
 9. Other clinically significant medical conditions that are not well controlled or for which medication needs are anticipated to change during the study.
 10. History of alcohol abuse or other substance abuse within 1 year prior to Day 0.

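### The primary composite and time to MELD ≥15 are tested without baseline MELD as a covariate, a valid plan that gives up power if MELD is prognostic within the randomization strata

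*Protocol*

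**What the plan says.** Protocol 13.1.3 fixes the primary test: "The 2 treatment groups will be compared using the log rank test stratified by the randomization stratification factor". The hazard ratio is taken from a Cox model stratified by the same randomization strata, and no covariates are named. Section 13.1.4 applies this method to time to first MELD ≥15, the first key secondary endpoint in the hierarchy of 13.1.10. The strata in 9.4 are UDCA treatment (yes/no) and mean baseline bilirubin (above ULN, or at or below it).

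MELD ≥15 is also a component of the primary composite. On its measurement, 12.2.6 says: "MELD scores and Child-Pugh score will be calculated at screening, and at all visits". At entry, 8.3 excludes subjects with "current MELD score >12", so a score of 12 is allowed.

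For change in ALP and total bilirubin, by contrast, the ANCOVA in 13.1.4 does include the baseline value as a covariate.

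**The concern.** A subject who enters at MELD 12 is 3 points from an event, and a subject with a low score is much further away. One cut on bilirubin captures only part of that spread. Within the upper stratum, mean bilirubin may range up to 5×ULN (8.2), screening creatinine up to 2 mg/dL is allowed (8.3), and the coagulation results that also enter MELD are not stratified.

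If MELD predicts events within strata, a log rank test that ignores it has less power than one that uses it. The trial is planned at 80% power over about 10 years in a rare disease, so a few points of power matter, and the covariate is already collected. A SAP could add a supportive adjusted model, but it could not make an adjusted test primary without departing from 13.1.3.

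**Working it through.** **Inputs from Protocol 13.1.2.** Test and level: "The 2 groups will be compared using a 2-sided log rank test at the 5% level of significance". Events and power: "a total of 127 events (both groups combined) will provide 80% power to demonstrate a statistically significant difference". Rates: "Exponential survival curves, placebo survival estimate of 0.6 at 8 years with a hazard ratio of 0.60, and total study duration of 10 years". Timing: "allowing for 4 years of subject accrual and 6 years of follow up". Allocation: "Subjects will be randomized in a 1:1 ratio to placebo or OCA". Dropout is 10% and N is 428. Section 13.1.12 adds looks at 64 and 96 events with Lan-DeMets O'Brien-Fleming boundaries.

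**Step 1: the plan's own figures.**
- Events, fixed design, Schoenfeld: 4(1.960 + 0.842)² / (ln 0.60)² = 31.4 / 0.261, which gives 121. Freedman: (1.960 + 0.842)² × (1.6/0.4)² gives 126.
- With looks at 64, 96 and 127 events, the bounds are 2.761, 2.290 and 2.045. Power at 127 events is 80.9% with the Schoenfeld drift and 79.2% with the Freedman drift. The stated 80% reproduces.
- Sample size: the placebo hazard is −ln(0.6)/8 = 0.0639 per year, and the OCA hazard is 0.6 times that. With uniform accrual over 4 years and 10 years in total, P(event) = 1 − (e^(−6λ) − e^(−10λ))/(4λ), which is 0.398 for placebo and 0.263 for OCA, 0.331 pooled. Then 127/0.331 = 384 and 384/0.90 = 427, against the stated 428.

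**Step 2: what adjustment would gain.** The protocol does not give the prognostic strength of MELD, so it is varied as an assumption. Each simulated trial has 428 subjects, stratified 1:1 randomization, 30% with bilirubin above ULN (the protocol's minimum), an assumed 90% on UDCA, dropout of 10% over 8 years, a MELD-conditional hazard ratio of 0.60, pooled placebo survival of 0.6 at 8 years, and analysis at the 127th event against the final bound of 2.0445. There are 2,500 runs per row. The overlap column is the share of MELD variance already carried by the bilirubin stratum.

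| Hazard per SD of MELD | Overlap | HR, strata only | HR, with MELD | Power, strata only | Power, with MELD | Difference (points) |
|---|---|---|---|---|---|---|
| 1.0 | 30% | 0.600 | 0.599 | 79.0% | 78.2% | −0.8 |
| 1.5 | 30% | 0.605 | 0.599 | 77.6% | 78.6% | +1.0 |
| 1.5 | 50% | 0.603 | 0.598 | 76.9% | 78.1% | +1.2 |
| 2.0 | 30% | 0.617 | 0.597 | 72.8% | 77.0% | +4.2 |
| 2.0 | 50% | 0.613 | 0.597 | 74.9% | 78.7% | +3.8 |
| 2.5 | 30% | 0.633 | 0.597 | 69.2% | 78.2% | +9.0 |
| 2.5 | 50% | 0.624 | 0.595 | 72.2% | 77.8% | +5.6 |

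Each power figure has a simulation standard error of about √(0.75 × 0.25/2500) = 0.9 points, so the differences at 1.0 and 1.5 are close to noise. Only the final look is scored, which is why the row without prognostic value lies slightly below 80.9%: a single test at 2.0445 has power Φ(½ × √127 × 0.511 − 2.0445) = Φ(0.83), about 80%.

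**The case against.** The strongest reply is that nothing here is stated wrongly. The sample size assumes a log rank test, the analysis is a log rank test, and bilirubin, which overlaps with MELD, is already a stratification factor. All of that stands. Three stronger readings are tempting, and the documents support none of them.

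- **That the trial is underpowered.** The strata-only powers of 69% to 78% in the prognostic rows arise because 0.60 was set there as the MELD-conditional hazard ratio. Section 13.1.2 does not say which hazard ratio it means. Read as the hazard ratio of the planned log rank test, 0.60 with 127 events gives the stated power.
- **That the planned hazard ratio is biased toward 1.** The strata-only and MELD-conditional hazard ratios are different quantities. The gap between them is non-collapsibility.
- **That chance imbalance in MELD would bias the comparison.** Under randomization it adds imprecision, which the test's error rate already covers.

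Three further limits hold. The prognostic strength is assumed, and the entry criteria restrict the spread of MELD. The 3-point argument concerns one component of the composite, and the protocol gives no component shares. The simulation uses a single composite hazard and a correctly specified score, not a MELD trajectory. The final bound also depends on the spending convention (about 2.016 or 2.044), which moves both power columns but not the contrast.

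It can also be said that 13.1.8 bars revising the primary analysis without regulatory agreement. That sentence concerns a switch to a comparison that includes historical controls. For a covariate it means at most a procedural step.

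**Conclusion.** The point holds as a loss of efficiency. The planned test controls type I error, and the 80% power is no arithmetic error. If baseline MELD is prognostic within strata, the plan forgoes about 1 power point at a hazard of 1.5 per SD, about 4 at 2.0, and 6 to 9 at 2.5. The direction is the same in every prognostic row, even with half of the MELD variance already in the bilirubin stratum. The size rests wholly on the assumed prognostic strength and is negligible at the low end. The plan's use of baseline values in its ANCOVA but not in its main time-to-event tests has no stated reason. The change is worth making because the covariate is already collected and the risk in using it is small.

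**What to change.** In 13.1.3, and for time to MELD ≥15 in 13.1.4, name baseline MELD as a covariate. Use a covariate-adjusted stratified log rank test, or the treatment test from the stratified Cox model with MELD included. Report the adjusted hazard ratio, and keep the unadjusted stratified log rank test as a sensitivity analysis. Fix this before the first unblinded interim analysis at 64 events, and with regulatory agreement.

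The change needs a protocol and SAP amendment but no new data, visits or subjects. The Cox hazard ratio becomes conditional on MELD, and the report should say so. The covariate-adjusted log rank test keeps the same null hypothesis and type I error as the planned test. If MELD proves not to be prognostic, under 1 power point is lost (79.0% against 78.2% in the simulation).
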